2.4. Analytical Methods

Measurement of oxfendazole plasma concentrations will be performed by the [name] Pharmacokinetics & Pharmacodynamics laboratory at the University of Iowa using a validated liquid chromatography-tandem mass spectrometry (LC/MS/MS) method for quantification of oxfendazole in human plasma with sodium heparin with lower limit of quantification (LLOQ) of 0.5 ng/mL.

Blood samples for PK analysis will be collected in tubes containing sodium heparin as the anticoagulant at baseline. The blood samples (10 mL) will be placed on ice after draw, and centrifuged within 1 hour at 4-8°C at approximately 3000 rpm for 15 minutes. The plasma will then be collected and stored frozen at -80°C until analyzed. Plasma samples will be shipped to the analytical lab frozen.

2.5. Collection of Pharmacodynamic or Clinical Endpoints

Not applicable.

3. PHARMACOKINETIC ANALYSIS METHODS

3.1. Analysis Populations and Handling of Missing Time Points

All subjects receiving study drug and having at least 1 measurable drug concentration will be included in the multiple ascending dose study PK population or the food effect study PK population, as appropriate. If there are subjects who do not have sufficient samples for a complete analysis, a modified analysis will be conducted in which some or all PK parameters may not be estimated for those subjects, but available PK concentrations will still be tabulated and graphed.

If any subjects are found to be noncompliant with respect to dosing, have incomplete data, or experience an event that is likely to affect PK, the Sponsor, the Investigator, and the Statistician will determine their inclusion into the population on a case-by-case basis. Subjects excluded from the PK analyses and their reasons for exclusion will be denoted and detailed.

PK sample concentrations identified as laboratory errors will be indicated as such in the report and may be excluded from analyses. Time points below the lower limit of quantification (LLOQ) preceding the first PK concentration above the LLOQ will be imputed as 0. Pharmacokinetically plausible concentration value(s) below LLOQ at time points between two measurable concentration values (e.g., at trough timepoints) will be replaced by the LLOQ/2 value for graphing purposes only, and treated as missing for analyses. All other PK sample concentrations below the LLOQ will be treated as missing for analyses. Missing PK sample concentrations will not be imputed for the NCA. A geometric mean of concentrations will be treated as missing for sets of data points containing a below the quantification limit (BQL) value.

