2.1.2 Human Phase I Safety and Pharmacokinetics

A recent dose escalation study has been performed evaluating 70 healthy adult men and women of non-child bearing potential who were age 18-45 (NCT02234570, DMID 12-0053, unpublished). Seven dose groups were studied (0.5, 1, 3, 7.5, 15, 30 and 60 mg/kg) and each dose group was comprised of 10 subjects of whom eight received study drug and two received placebo. All subjects received a single dose of study drug or placebo and were followed for 14 days for safety and the pharmacokinetics of oxfendazole and metabolites including fenbendazole and oxfendazole sulfone were evaluated in blood and urine. There were no study drug associated serious adverse events identified. Sixteen unsolicited adverse events were experienced by 10 subjects. Six were considered related to the study treatment. Five of the events were mild and included one subject with an increased PR interval 14 days following the dose of study drug, and the remaining events were gastrointestinal events (nausea, loose stools, intestinal gas, and diarrhea, all of which occurred in the 30 or 60 mg/kg dose groups. There was one event, a sore throat that was considered moderate in intensity. Mild to moderate laboratory events were seen in hematology and chemistry tests. There were no patterns identified related to timing of the abnormal laboratory studies or dose of oxfendazole and the placebo group had similar rates of abnormal laboratory values.

The median time of maximum concentration (T_{max}) occurred at 2 hours and the geometric mean maximum concentration (C_{max}) ranged from 943.9-6768.4 ng/mL. The exposure was non-linear, plateauing at 15 mg/kg. The half-life ($t_{1/2}$) was consistent between groups and ranged from 8.5-11 hours. The overall fraction of drug excreted in the urine was very low and the geometric mean AUC_{0-t} for the sulfone metabolite was 11.5-15% of oxfendazole AUC_{0-t} while fenbendazole AUC_{0-t} was less than 1% of oxfendazole AUC_{0-t} for each dose group.

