- Perform a urine pregnancy test for females of childbearing potential.
- A targeted physical exam may be performed, if indicated.
- Review concomitant medications
- Review for AEs and SAEs
- A heparin lock will be inserted, blood will be drawn (10 mL) for baseline PK (prior to product administration)

Administration of Study Medication

A study nurse will administer a single 3 mg/kg oral dose of oxfendazole to the subject.

- For subjects who fasted during the first day of study drug administration, provide high fat breakfast prior to study drug administration. Approximately 30 minutes (+/- 15 minutes) following completion of the meal, the study nurse will administer a single 3 mg/kg oral dose of oxfendazole.
- For subjects who received a meal prior to the first day of study drug administration, subjects should fast for 8 hours prior to receipt of study drug and remain fasting (water is permitted) for two hours after the administration of drug.
- Lunch and dinner will be provided. Subjects will be allowed to eat snacks but will be asked to avoid drinking grapefruit juice and excessive (>2 cups) coffee.
- 10 mL of blood for oxfendazole level will be drawn at 30 minutes, 1, 2, 3, 4, 6, 9, and 12 hours (all times have a window of +/- 15 minutes except the 9 and 12 hour samples which have a window of +/- 30 minutes- it is critical to record the exact time of blood draw).
- Perform EKG approximately 2 hours following study drug (+/- 20 minutes)
- Assess AEs and SAEs throughout the day and prior to discharge from the CRU.
- Counsel on need to avoid alcohol, drugs, tobacco and medications throughout the study.
- Counseling on avoidance of pregnancy.

Clinic Visit 05, Day 9: (or 1 day following second dose)

- Vital signs including oral temperature, blood pressure, and pulse will be obtained.
- A targeted physical exam may be performed, if indicated.
- Review concomitant medications
- Review for AEs and SAEs

-
- Draw 10 mL of blood for oxfendazole level -approximately 24 hours after dosing on day 8 (+/- 2 hours)
 - Counsel on need to avoid alcohol, drugs, tobacco and medications throughout the study.

7.7 Final Study Visit 06 Day 14 (+/- 2 days) - GROUP 4

- Vital signs including oral temperature, blood pressure, and pulse will be obtained.
- A targeted physical exam may be performed, if indicated.
- Review concomitant medications
- Review for AEs and SAEs
- Draw 10 mL of blood for oxfendazole level

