2.3. PK Sampling Schedule Treatment Groups

For the first phase of the study (Groups 1-3), 10 mL of blood for oxfendazole level will be drawn pre-dose and at 30 minutes, 1, 2, 3, 4, 6, 9, and 12 hours following the first dose. All times have a window of +/- 15 minutes except the 9 and 12 hour samples which have a window of +/- 30 minutes. On Days 2, 3, and 4, blood will be sampled for oxfendazole level approximately 24 hours (+/- 4 hours for Day 2, +/- 2 hours for Days 3 and 4) after the prior dose, but before the current study day dose. On Days 2, 3, and 4, approximately 2 hours (+/- 20 minutes) after administration of study drug, blood will be drawn for oxfendazole level. On Day 5, blood will be sampled pre-dose (24 hours +/- 2 hours after the prior dose) and at 30 minutes, 1, 2, 3, 4, 6, 9, and 12 hours (all times have a window of +/- 15 minutes except the 9 and 12 hour samples which have a window of +/- 30 minutes). Blood will also be sampled for oxfendazole level on Day 6, approximately 24 hours after dosing on Day 5 (+/- 6 hours) and Days 8 (+/- 1 day) and 10 (+/- 2 days).

In the second phase of the study (Group 4), blood sampling for oxfendazole level will be performed pre-dose and at 30 minutes, 1, 2, 3, 4, 5, 9, 12 and 24 hours following each dose on Day 1 and Day 8 (+/- 1 day). All times have a window of +/- 15 minutes except the 9 and 12

hour samples which have a window of \pm 0 minutes and the 24-hour sample which has a window of \pm 4 hours. Blood will also be sampled for oxfendazole level on Day 14 (\pm 0 days).

The exact time for all blood draws for oxfendazole level will be recorded and used for pharmacokinetic noncompartmental analysis (NCA).

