| | Nominal Time After Dose 5 (hours) | | | | | | | | | | | | | |
|------------|-----------------------------------|--------|--------|--------|--------|--------|--------|--------|--------|--------|--------|--------|--|--|
| Subject ID | Pre-dose | .5 | 1 | 2 | 3 | 4 | 6 | 9 | 12 | 24 | 72 | 120 | | |
| 99ZZZ001 | X | х | х | х | х | х | х | х | х | х | х | Х | | |
| 99ZZZ002 | X | х | х | х | Х | Х | х | х | х | х | х | х | | |
| 99ZZZ003 | X | Х | х | х | X | х | х | х | х | х | х | х | | |
| | X | Х | х | х | х | X | х | Х | х | х | х | Х | | |
| Statistic | | | | | | | | | | | | | | |
| N^1 | X | Х | Х | Х | Х | X | Х | Х | Х | х | х | х | | |
| Mean | X.X | X.X | x.x | x.x | x.x | x.x | X.X | X.X | x.x | x.x | x.x | X.X | | |
| SD | X.X | X.X | X.X | X.X | X.X | x.x | X.X | X.X | X.X | x.x | x.x | x.x | | |
| GM | X.X | X.X | x.x | x.x | x.x | x.x | X.X | X.X | x.x | x.x | x.x | x.x | | |
| (Min, Max) | (x, x) | (x, x) | (x, x) | (x, x) | (x, x) | (x, x) | (x, x) | (x, x) | (x, x) | (x, x) | (x, x) | (x, x) | | |

¹ Number of data points used to compute the summary statistics. BQL values were imputed as 0 if they did not come after a PK sample concentration that is above the LLOQ and treated as missing otherwise.

Table 7: Individual Concentrations and Summary Statistics by Nominal Time: Group 2 (7.5 mg/kg), Dose 5

Table 8: Individual Concentrations and Summary Statistics by Nominal Time: Group 3 (15 mg/kg), Dose 5

Table 7 and **Table 8** will use the form of **Table 6** to display corresponding data for Group 2 and Group 3.

Table 9: Peak and Trough Concentrations by Dose: Group 1 (3 mg/kg)

| | Dose 1 | | Dose 2 | | Dos | se 3 | Dos | se 4 | Dose 5 | |
|------------|-------------------|---------------------|--------|--------|--------|--------|--------|--------|--------|--------|
| | Peak ¹ | Trough ² | Peak | Trough | Peak | Trough | Peak | Trough | Peak | Trough |
| 99ZZZ001 | X | Х | X | X | X | Х | X | x | X | X |
| 99ZZZ002 | Х | х | Х | х | X | Х | Х | х | Х | х |
| 99ZZZ003 | X | Х | X | X | X | X | X | х | X | X |
| | X | Х | X | X | X | Х | X | х | X | X |
| Statistic | | | | | | | | | | |
| N^3 | X | X | X | X | X | X | X | X | X | X |
| Mean | x.x | x.x | x.x | X.X | x.x | X.X | X.X | X.X | X.X | X.X |
| SD | x.x | x.x | x.x | X.X | x.x | X.X | X.X | X.X | X.X | X.X |
| GM | x.x | x.x | x.x | x.x | x.x | x.x | X.X | X.X | X.X | X.X |
| (Min, Max) | (x, x) | (x, x) | (x, x) | (x, x) | (x, x) | (x, x) | (x, x) | (x, x) | (x, x) | (x, x) |

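### By-time concentration summaries drop late values below the LLOQ, and pool draws up to two (Day 8) or four (Day 10) days apart as one nominal time

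*SAP*

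**What the plan says.** SAP 2.4 gives a "lower limit of quantification (LLOQ) of 0.5 ng/mL". SAP 3.1 sets BQL values before the first measurable one to 0. For those after the last measurable value it says: "All other PK sample concentrations below the LLOQ will be treated as missing for analyses". The footnote to each by-time table in SAP Appendix I repeats this: BQL values are "imputed as 0 if they did not come after a PK sample concentration that is above the LLOQ and treated as missing otherwise".

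For one statistic SAP 3.1 adds a safeguard: "A geometric mean of concentrations will be treated as missing for sets of data points containing a below the quantification limit (BQL) value". Nothing similar is stated for the arithmetic mean, SD or minimum.

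Table 6 (and Tables 7-8, which take its form) prints N, mean, SD, geometric mean and min/max by nominal time, with columns at 72 h and 120 h after Dose 5. Table 13 (and Table 15) adds a 144 h column for the second Group 4 dose. Figures 3 and 9 plot arithmetic means with SD bars.

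SAP 2.3 allows the late draws on "Days 8 (+/- 1 day) and 10 (+/- 2 days"; Protocol 7.3, 7.4 and Appendix A give the same windows. For Group 4, Protocol 7.7 has "Day 14 (+/- 2 days) - GROUP 4", while the SAP text as read shows a window of zero days.

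**The concern.** A BQL result after the peak is an observed low value, not an absent one. Removing only the lowest values from a column leaves a mean and minimum that describe the subjects who eliminate slowly or came in early. The SAP recognises this for the geometric mean but leaves the arithmetic summaries exposed.

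The visit windows add a second problem. A draw two days before nominal and one two days after it enter the same column although they lie several half-lives apart, and no rule moves or removes an in-window draw. The two faults compound, because late in-window draws are the likeliest to be dropped.

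At stake is the accuracy of the late columns. Protocol 11.1 assesses multi-dose kinetics descriptively, so these tables are part of what is reported for that secondary objective.

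**Working it through.** The documents state no figure on this point, so there is none to reproduce first. The nominal times do follow from the schedule: (8-5)×24 = 72 h, (10-5)×24 = 120 h, (14-8)×24 = 144 h.

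**Inputs from the documents.** LLOQ 0.5 ng/mL (SAP 2.4). Half-life in the previous single-dose study "ranged from 8.5-11 hours" (Protocol 2.1.2). Geometric mean Cmax 943.9 to 6768.4 ng/mL over all doses from 0.5 to 60 mg/kg, median Tmax 2 h (same section). No Cmax by dose is given, so the range serves as a bracket. Eight subjects per group in Groups 1-3, six per sequence in Group 4.

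**Assumptions not in the documents.** Between-subject CV 20% for half-life and 40% for Cmax; mono-exponential decline from Cmax at 2 h.

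**Step 1: direction.** Every dropped value is below 0.5 and every retained value is at least 0.5. Hence the mean of the retained values exceeds the mean of all true values whenever any is dropped, and the printed minimum cannot fall below 0.5. If k of n values are BQL, the retained mean is exactly n/(n-k) times the mean with BQL set to 0. For n = 8 this is 8/7 = 1.14 at k = 1, 2 at k = 4 and 8 at k = 7.

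**Step 2: where BQL values are expected.** After Dose 5, C(t) = Cmax × AR × exp(-λ(t-2)), with λ = ln 2 / half-life and the SAP's AR = 1/(1-exp(-24λ)). After one Group 4 dose AR is left out.
- 72 h: 3.6 (Cmax 943.9, half-life 8.5) to 105 ng/mL (6768.4, 11), above the LLOQ.
- 120 h: 0.07 to 5.1 ng/mL, straddling it.
- 144 h after a single dose: 0.009 to 0.88 ng/mL, mostly below it.

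**Step 3: size of the dropping bias at 120 h.** Simulated, n = 8, all draws exactly on time. The entries are median means in ng/mL; the first column is taken over data sets with at least one measurable value.

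| Cmax, half-life | BQL share | BQL dropped | BQL = 0 | Ratio |
|---|---|---|---|---|
| 943.9, 8.5 h | 85% | 1.06 | 0.13 | 8.2 |
| 943.9, 11 h | 42% | 2.48 | 1.46 | 1.7 |
| 6768.4, 8.5 h | 49% | 2.95 | 1.50 | 2.0 |
| 6768.4, 11 h | 10% | 12.26 | 11.08 | 1.1 |

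Setting BQL to 0 itself understates a little. Against the simulated true mean at 120 h (0.22, 1.54, 1.58 and 11.09) the ratios are 4.8, 1.6, 1.9 and 1.1. At 72 h dropping adds 0 to 8%. At 144 h in Group 4 (n = 6), starting levels of 943.9 and 2,500 ng/mL give a BQL share of 60 to 98%.

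**Step 4: the windows.** Day 7 to 9 is 48-96 h after Dose 5, and Day 8 to 12 is 72-168 h. The two overlap from 72 to 96 h. Within one subject the concentration changes by 2^(width/half-life):
- Day 8, 48 h wide: 2^(48/11) = 21 to 2^(48/8.5) = 50-fold.
- Day 10, 96 h wide: 2^(96/11) = 424 to 2^(96/8.5) = 2,511-fold.

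If each whole day in the window is equally likely, dropping and pooling together give a reported 120 h mean of 3.52, 8.62, 15.65 and 44.26 ng/mL, against 0.22, 1.53, 1.57 and 10.96 at a true 120 h: 4 to 16 times. At 72 h the same exercise gives 1.7 to 2.6 times, nearly all from timing.

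**The case against.** The strongest reply is that no conclusion of the trial rests on these cells. The PK endpoints are Cmax, Tmax, AUC and half-life. SAP 3.4 estimates them from actual times, and AUC_last ends at the last value at or above the LLOQ. A reader might infer that AUC, half-life, the food-effect intervals or dose proportionality are biased too. The documents do not support that: none of these uses the 72, 120 or 144 h means.

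A reader might also infer that every tail summary is inflated. That goes too far. The geometric mean is withheld rather than biased, so dropping cannot lift a tail point in the semi-log mean plots (Figures 4 and 10). The by-time tables print no median. On the linear scale of Figures 3 and 9, with peaks in the thousands, a dropping error of about 1 ng/mL cannot be seen. The mock-ups are not reproduced, so how far those curves extend is unknown. Nor will the full 424-2,511-fold spread appear in print: with values below 0.5 removed, typical 72 h levels of 3.6 to 105 ng/mL leave about 7-fold (3.6/0.5) to 210-fold (105/0.5).

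The plan is also open about its rule. The footnote states it, N is printed, individual values stand above the summary, and Listing 3 gives actual times, with BQL and out-of-window samples flagged under SAP 3.3.

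All of this stands and keeps the point small. It does not answer it. N alone does not separate a BQL result from a missed draw, a sample two days off nominal counts as within window, and the printed arithmetic mean is still wrong.

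**Conclusion.** The point holds for the descriptive by-time tables and the arithmetic mean plots. When post-peak BQL values occur, the late arithmetic mean and minimum are too high and the SD is distorted. This matters at 120 h and 144 h; at 72 h the window, not the dropping, is the problem.

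The upward direction and the fold ranges across the windows follow from the plan's rule, its windows and the documented half-life. The size of the dropping bias, about 1.1 to 8 times at 120 h relative to BQL set to 0, rests on the assumed CVs and on a Cmax bracket that is not specific to dose. The 4-to-16-fold combined figure also assumes that the whole window is used evenly; visits kept near nominal would give less. Nominal-time pooling does not touch the NCA parameters.

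**What to change.** For by-time concentration summaries only, amend SAP 3.1 and the table footnotes:
- Print the number BQL at each time point.
- When post-peak BQL values are present, either withhold the arithmetic mean and SD, as is already done for the geometric mean, or compute them with BQL set to 0 (LLOQ/2 as sensitivity) and show the minimum as BQL. With 0, the mean is understated by less than 0.5 ng/mL times the BQL share.
- Leave the existing BQL rule unchanged for NCA and the model-based analyses.
- Show Day 8, 10 and 14 samples individually at actual time. Average only draws close to nominal, within a tolerance that the sponsor fixes in advance.
- Reconcile the Day 14 window between Protocol 7.7 and SAP 2.3, unless the SAP's zero is a fault of the PDF reading. The same sentence group also shows a zero window for the 9 h and 12 h samples, which suggests such a fault.

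The cost is SAP wording and table programming. The downside is that some late cells will average fewer values or show no mean.

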3.2. Demographic and Baseline Characteristics

Sex, race, age, weight, height, and body mass index (BMI) of subjects in the PK population will be listed and summarized by treatment group (Listing 1, Table 1, and Table 2).

3.3. Dosing and Pharmacokinetic Sampling Summary

Subject dose administration times will be presented (Listing 2). Special cases that potentially affect the analysis will be discussed. Drug plasma concentrations will be listed by group and subject, with BQL, out of sample time window, and PK analyses-excluded samples indicated (Listing 3). The listings will also indicate, for each sample, the associated dose number, nominal and actual time since first dose, and actual time since the preceding dose.

Important protocol deviations related to dosing or PK sampling will be discussed. Potentially important bioanalytical errors and their effect on the PK analysis will also be discussed.

For Groups 1-3, Table 3, Table 4, and Table 5 will list and summarize drug concentrations for Dose 1 and Table 6, Table 7, and Table 8 will summarize drug concentrations for Dose 5. As only peak and trough concentrations are measured for doses 2-4, these concentrations will be

displayed in Table 9, Table 10, and Table 11. For Group 4, Table 12, Table 13, Table 14, and Table 15 will list and summarize drug concentrations by sequence and period.

The following figures will display concentration data for the multiple ascending dose phase (Groups 1-3):

- Linear scale concentration profiles of all subjects, color-coded by dose group (Figure 1)
- Linear plot of mean concentration for each dose group over time, with error bars representing standard deviation, color-coded by dose group (Figure 3)
- Linear scale concentration profile for each subject individually, repeated for all subjects (Figure 5)
- Data from Figures 1, 3 and 5 will be presented on a semi-log scale in Figure 2, Figure 4, and Figure 6.

The following figures will display concentration data for the second phase evaluating food effects (Group 4):

- Linear scale concentration profiles of all subjects, displayed by sequence and period (Figure 7)
- Linear plot of mean concentration for each condition over time, with error bars representing standard deviation, color-coded by condition (Figure 9)
- Linear scale concentration profile of each condition for each subject individually, repeated for all subjects (Figure 11)
- Data from Figure 7, Figure 9, and Figure 11 will be presented on a semi-log scale in Figure 8, Figure 10 and Figure 12.

3.4. Definition and Estimation of Individual PK Parameters

The PK parameters listed below will be estimated through a NCA using version 8.0 of Phoenix WinNonlin (Pharsight Corporation, Cary, NC). Actual post-dose time will be used for the estimation of PK parameters instead of nominal time. Subject-specific PK parameters will be presented (Table 16, Table 17, Table 18, Table 19, Table 20, Table 21, Table 22 Table 27, Listing 3, Listing 4, and Listing 5).

Phoenix WinNonlin NCA will use the following settings to compute parameters from plasma PK data:

- Linear Up Log Down calculation method
- Uniform weighting
- Extravascular dose
- Lambda Z Acceptance Criteria
 - o Rsq adjusted ≥ 0.85
 - Span ≥ 1.5 half-lives

\mathbf{C}_{max}

Maximum concentration (C_{max}) is defined as the maximum observed drug concentration observed over all PK sample concentrations for a given dose, and will be obtained from the **Cmax** parameter calculated by Phoenix WinNonlin.

Ctrough

Pre-dose trough concentration (C_{trough}) is defined as the drug concentration observed at the last planned timepoint prior to dosing. Since there is no dose following Day 5, C_{trough} for that day is defined as the concentration 24 hours (nominal time) after dosing.

Tmax

Time of maximum concentration (T_{max}) is defined as the time at which the maximum concentration occurs within the given dosing interval and will be obtained from the **Tmax** parameter calculated by Phoenix WinNonlin.

λ_z

The terminal phase elimination rate constant (λ_z) is defined as the first-order rate constant describing the rate of decrease of drug concentration in the terminal phase (defined as the terminal region of the PK curve where drug concentration follows first-order elimination kinetics), and will be obtained from the **Lambda z** parameter calculated by Phoenix WinNonlin.

 λ_z will be computed as the slope of a terminal region consisting of at least 3 successive points in the plot of log-transformed concentration data versus time. λ_z will be estimated using uniform weighting. Time points used in the estimation of λ_z will be initially selected using the Phoenix WinNonlin automatic algorithm. The set of points chosen must contain only timepoints after T_{max} , include at least 3 timepoints, and satisfy the Lambda Z Acceptance Criteria described above. The range of concentrations used to estimate λ_z for each profile will be inspected by the PK analyst, and the PK analyst may adjust the set of concentrations used to estimate λ_z if deemed necessary, but manually selected ranges must satisfy the same acceptance criteria as those chosen automatically by the Phoenix WinNonlin algorithm.

Drug concentrations used to calculate λ_z will be indicated in Listing 3.

 λ_z will be estimated for Doses 1 and 5 in Groups 1, 2, and 3, and for Group 4.

t½

The apparent terminal elimination half-life $(t_{1/2})$ is defined as the time required for the drug concentration to decrease by a factor of one-half in the terminal phase. The apparent terminal elimination half-life $(t_{1/2})$ will be estimated as $\ln(2)/\lambda_z$ and will be obtained from the **HL_Lambda_z** parameter calculated by Phoenix WinNonlin. $t_{1/2}$ will be estimated for Doses 1 and 5 in Groups 1, 2, and 3, and for Group 4, when λ_z is estimable.

AUC

AUC is defined as the area under the concentration-time curve. AUC will be estimated using the Linear Up Log Down calculation method.

AUC_{τ}

 AUC_{τ} is defined as AUC of a single dosing period. In groups 1-3, AUC_{τ} for a given dose will be calculated as AUC from time of dosing to the end of the 24-hour dosing interval for Dose 1 and Dose 5. AUC_{τ} will be obtained in Phoenix WinNonlin using the Partial Area functionality.

AUClast

AUC_{last} is defined as the AUC from dosing to the time of the last measured concentration \geq LLOQ (C_{last}) of that dosing period and will be obtained from the **AUClast** parameter calculated by Phoenix WinNonlin.

AUC (0-∞)

AUC $_{(0-\infty)}$ is defined as the AUC from dosing taken to the limit as the end time becomes arbitrarily large. AUC $_{(0-\infty)}$ for a given dose will be estimated by adding AUC $_{last}$ for that dose to an extrapolated value equal to the last measured concentration greater than the LLOQ divided by λ_z :

$$AUC_{(0-\infty)} = AUC_{last} + \frac{C_{last}}{\lambda_z},$$

where C_{last} is the last measured concentration \geq LLOQ. $AUC_{(0-\infty)}$ will be obtained from the $\mathbf{AUCINF_obs}$ parameter calculated by Phoenix WinNonlin If the amount extrapolated portion of $AUC_{(0-\infty)}$ is >25%, the estimated $AUC_{(0-\infty)}$ value will be flagged when listed in the report and will be excluded from downstream statistical analyses, but included in the calculation of summary statistics.

 AUC_{τ} , will be estimated for Dose 1 and Dose 5 in Groups 1, 2, and 3. AUC_{last} will be estimated for Dose 5 in Groups 1, 2 and 3, and for Group 4. $AUC_{(0-\infty)}$ will be estimated for Group 4 when λ_z is estimable.

CL/F

For Group 4, apparent oral clearance (CL/F) will be calculated as Dose/AUC_(0- ∞) and will be obtained from the **CL_F** parameter in Phoenix WinNonlin. If the amount extrapolated portion of AUC_(0- ∞) is >25%, the estimated CL/F value will be flagged when listed in the report, but included in the calculation of summary statistics.

CLss/F

For Groups 1, 2 and 3, apparent oral clearance at steady state (CL_{SS}/F) will be calculated as the dose in mg/kg divided by the AUC_{τ} for Dose 5 (expected steady state) and will be obtained from the $Clss_F$ parameter calculated by Phoenix WinNonlin.

$$CL_{SS}/F = \frac{Dose}{AUC_{\tau, Dose 5}}$$

V_d/F

For Group 4, apparent volume of distribution (V_d/F) will be calculated as (CL/F)/ λ_z and will be obtained from the \mathbf{Vz}_F parameter in Phoenix WinNonlin. If the amount extrapolated portion of $AUC_{(0-\infty)}$ is >25%, the estimated V_d/F value will be flagged when listed in the report, but included in the calculation of summary statistics.

AR

For Groups 1, 2 and 3, the observed accumulation ratio (AR) is defined as the ratio of exposure parameters following multiple and single dosing. AR will be calculated using AUC_{τ} and C_{max} :

$$AR = \frac{AUC_{\tau, Dose 5}}{AUC_{\tau, Dose 1}},$$

$$AR = \frac{C_{\text{max, Dose 5}}}{C_{\text{max, Dose 1}}}$$

When λ_Z is estimable, AR will also be estimated using the elimination rate λz from Dose 5:

$$AR = \frac{1}{1 - e^{-\lambda_Z \tau}},$$

where τ is the length of the dosing interval, 24 hours.

